## 11. MEASUREMENT OF EFFECT

### 11.1 Antitumor Effect – Solid Tumors

For the purposes of this study, patients should be re-evaluated for response every 8 weeks. In addition to a baseline scan, confirmatory scans should also be obtained 4 (not less than 4) weeks following initial documentation of objective response.

Response and progression will be evaluated in this study using the new international criteria proposed by the revised Response Evaluation Criteria in Solid Tumors (RECIST) guideline (version 1.1) [*Eur J Ca* 45:228-247, 2009]. Changes in the largest diameter (unidimensional measurement) of the tumor lesions and the shortest diameter in the case of malignant lymph nodes are used in the RECIST criteria.

#### 11.1.1 Definitions

Evaluable for toxicity. All patients will be evaluable for toxicity from the time of their first treatment with MLN0128 (TAK-228).

Evaluable for objective response. Only those patients who have measurable disease present at baseline, have received at least one cycle of therapy, and have had their disease re-evaluated will be considered evaluable for response. These patients will have their response classified according to the definitions stated below. (Note: Patients who exhibit objective disease progression prior to the end of cycle 1 will also be considered evaluable.)

Evaluable Non-Target Disease Response. Patients who have lesions present at baseline that are evaluable but do not meet the definitions of measurable disease, have received at least one cycle of therapy, and have had their disease re-evaluated will be considered evaluable for non-target disease. The response assessment is based on the presence, absence, or unequivocal progression of the lesions.

#### 11.1.2 Disease Parameters

Measurable disease. Measurable lesions are defined as those that can be accurately measured in at least one dimension (longest diameter to be recorded) as  $\geq 20$  mm ( $\geq 2$  cm) by chest x-ray or as  $\geq 10$  mm ( $\geq 1$  cm) with CT scan, MRI, or calipers by clinical exam. All tumor measurements must be recorded in millimeters (or decimal fractions of centimeters).

Note: Tumor lesions that are situated in a previously irradiated area might or might not be considered measurable.

Malignant lymph nodes. To be considered pathologically enlarged and measurable, a lymph node must be  $\geq 15$  mm ( $\geq 1.5$  cm) in short axis when assessed by CT scan (CT scan

slice thickness recommended to be no greater than 5 mm [0.5 cm]). At baseline and in follow-up, only the short axis will be measured and followed.

Non-measurable disease. All other lesions (or sites of disease), including small lesions (longest diameter <10 mm [<1 cm] or pathological lymph nodes with  $\geq 10$  to <15 mm [ $\geq 1$  to <1.5 cm] short axis), are considered non-measurable disease. Bone lesions, leptomeningeal disease, ascites, pleural/pericardial effusions, lymphangitis cutis/pulmonitis, inflammatory breast disease, and abdominal masses (not followed by CT or MRI), are considered as non-measurable.

Note: Cystic lesions that meet the criteria for radiographically defined simple cysts should not be considered as malignant lesions (neither measurable nor non-measurable) since they are, by definition, simple cysts.

‘Cystic lesions’ thought to represent cystic metastases can be considered as measurable lesions, if they meet the definition of measurability described above. However, if non-cystic lesions are present in the same patient, these are preferred for selection as target lesions.

Target lesions. All measurable lesions up to a maximum of 2 lesions per organ and 5 lesions in total, representative of all involved organs, should be identified as **target lesions** and recorded and measured at baseline. Target lesions should be selected on the basis of their size (lesions with the longest diameter), be representative of all involved organs, but in addition should be those that lend themselves to reproducible repeated measurements. It may be the case that, on occasion, the largest lesion does not lend itself to reproducible measurement in which circumstance the next largest lesion which can be measured reproducibly should be selected. A sum of the diameters (longest for non-nodal lesions, short axis for nodal lesions) for all target lesions will be calculated and reported as the baseline sum diameters. If lymph nodes are to be included in the sum, then only the short axis is added into the sum. The baseline sum diameters will be used as reference to further characterize any objective tumor regression in the measurable dimension of the disease.

Non-target lesions. All other lesions (or sites of disease) including any measurable lesions over and above the 5 target lesions should be identified as **non-target lesions** and should also be recorded at baseline. Measurements of these lesions are not required, but the presence, absence, or in rare cases unequivocal progression of each should be noted throughout follow-up.

### 11.1.3 Methods for Evaluation of Measurable Disease

All measurements should be taken and recorded in metric notation using a ruler or calipers. All baseline evaluations should be performed as closely as possible to the beginning of treatment and never more than 4 weeks before the beginning of the treatment.

The same method of assessment and the same technique should be used to characterize each identified and reported lesion at baseline and during follow-up. Imaging-based evaluation is preferred to evaluation by clinical examination unless the lesion(s) being followed cannot be imaged but are assessable by clinical exam.

Clinical lesions Clinical lesions will only be considered measurable when they are superficial (*e.g.*, skin nodules and palpable lymph nodes) and  $\geq 10$  mm ( $\geq 1$  cm) diameter as assessed using calipers (*e.g.*, skin nodules). In the case of skin lesions, documentation by color photography, including a ruler to estimate the size of the lesion, is recommended.

Chest x-ray Lesions on chest x-ray are acceptable as measurable lesions when they are clearly defined and surrounded by aerated lung. However, CT is preferable.

Conventional CT and MRI This guideline has defined measurability of lesions on CT scan based on the assumption that CT slice thickness is 5 mm (0.5 cm) or less. If CT scans have slice thickness greater than 5 mm (0.5 cm), the minimum size for a measurable lesion should be twice the slice thickness. MRI is also acceptable in certain situations (*e.g.* for body scans).

Use of MRI remains a complex issue. MRI has excellent contrast, spatial, and temporal resolution; however, there are many image acquisition variables involved in MRI, which greatly impact image quality, lesion conspicuity, and measurement. Furthermore, the availability of MRI is variable globally. As with CT, if an MRI is performed, the technical specifications of the scanning sequences used should be optimized for the evaluation of the type and site of disease. Furthermore, as with CT, the modality used at follow-up should be the same as was used at baseline and the lesions should be measured/assessed on the same pulse sequence. It is beyond the scope of the RECIST guidelines to prescribe specific MRI pulse sequence parameters for all scanners, body parts, and diseases. Ideally, the same type of scanner should be used and the image acquisition protocol should be followed as closely as possible to prior scans. Body scans should be performed with breath-hold scanning techniques, if possible.

PET-CT At present, the low dose or attenuation correction CT portion of a combined PET-CT is not always of optimal diagnostic CT quality for use with RECIST measurements. However, if the site can document that the CT performed as part of a PET-CT is of identical diagnostic quality to a diagnostic CT (with IV and oral contrast), then the CT portion of the PET-CT can be used for RECIST measurements and can be used interchangeably with conventional CT in accurately measuring cancer lesions over time. Note, however, that the PET portion of the CT introduces additional data which may bias an investigator if it is not routinely or serially performed.

Ultrasound Ultrasound is not useful in assessment of lesion size and should not be used as a method of measurement. Ultrasound examinations cannot be reproduced in their

entirety for independent review at a later date and, because they are operator dependent, it cannot be guaranteed that the same technique and measurements will be taken from one assessment to the next. If new lesions are identified by ultrasound in the course of the study, confirmation by CT or MRI is advised. If there is concern about radiation exposure at CT, MRI may be used instead of CT in selected instances.

Endoscopy, Laparoscopy The utilization of these techniques for objective tumor evaluation is not advised. However, such techniques may be useful to confirm complete pathological response when biopsies are obtained or to determine relapse in trials where recurrence following complete response (CR) or surgical resection is an endpoint.

Tumor markers Tumor markers alone cannot be used to assess response. If markers are initially above the upper normal limit, they must normalize for a patient to be considered in complete clinical response. Specific guidelines for both CA-125 response (in recurrent ovarian cancer) and PSA response (in recurrent prostate cancer) have been published [*JNCI* 96:487-488, 2004; *J Clin Oncol* 17, 3461-3467, 1999; *J Clin Oncol* 26:1148-1159, 2008]. In addition, the Gynecologic Cancer Intergroup has developed CA-125 progression criteria which are to be integrated with objective tumor assessment for use in first-line trials in ovarian cancer [*JNCI* 92:1534-1535, 2000].

Cytology, Histology These techniques can be used to differentiate between partial responses (PR) and complete responses (CR) in rare cases (*e.g.*, residual lesions in tumor types, such as germ cell tumors, where known residual benign tumors can remain).

The cytological confirmation of the neoplastic origin of any effusion that appears or worsens during treatment when the measurable tumor has met criteria for response or stable disease is mandatory to differentiate between response or stable disease (an effusion may be a side effect of the treatment) and progressive disease.

#### 11.1.4 Response Criteria

##### 11.1.4.1 Evaluation of Target Lesions

Complete Response (CR): Disappearance of all target lesions. Any pathological lymph nodes (whether target or non-target) must have reduction in short axis to <10 mm (<1 cm).

Partial Response (PR): At least a 30% decrease in the sum of the diameters of target lesions, taking as reference the baseline sum diameters.

Progressive Disease (PD): At least a 20% increase in the sum of the diameters of target lesions, taking as reference the smallest sum on study (this includes the baseline sum if that is the smallest on study). In addition to the relative increase of 20%, the sum must also demonstrate an absolute increase of at least 5 mm (0.5 cm).

(Note: the appearance of one or more new lesions is also considered progressions).

Stable Disease (SD): Neither sufficient shrinkage to qualify for PR nor sufficient increase to qualify for PD, taking as reference the smallest sum diameters while on study.

#### 11.1.4.2 Evaluation of Non-Target Lesions

Complete Response (CR): Disappearance of all non-target lesions and normalization of tumor marker level. All lymph nodes must be non-pathological in size (<10 mm [ $<1$  cm] short axis).

Note: If tumor markers are initially above the upper normal limit, they must normalize for a patient to be considered in complete clinical response.

Non-CR/Non-PD: Persistence of one or more non-target lesion(s) and/or maintenance of tumor marker level above the normal limits.

Progressive Disease (PD): Appearance of one or more new lesions and/or *unequivocal progression* of existing non-target lesions. *Unequivocal progression* should not normally trump target lesion status. It must be representative of overall disease status change, not a single lesion increase.

Although a clear progression of “non-target” lesions only is exceptional, the opinion of the treating physician should prevail in such circumstances, and the progression status should be confirmed at a later time by the review panel (or Principal Investigator).

#### 11.1.4.3 Evaluation of Best Overall Response

The best overall response is the best response recorded from the start of the treatment until disease progression/recurrence (taking as reference for progressive disease the smallest measurements recorded since the treatment started). The patient's best response assignment will depend on the achievement of both measurement and confirmation criteria.

#### For Patients with Measurable Disease (*i.e.*, Target Disease)

Target Lesions	Non-Target Lesions	New Lesions	Overall Response	Best Overall Response when Confirmation is Required*
CR	CR	No	CR	$\geq 4$ wks. Confirmation**
CR	Non-CR/Non-PD	No	PR	
CR	Not evaluated	No	PR	

PR	Non-CR/Non-PD/not evaluated	No	PR	≥4 wks. Confirmation**
SD	Non-CR/Non-PD/not evaluated	No	SD	Documented at least once ≥4 wks. from baseline**
PD	Any	Yes or No	PD	no prior SD, PR or CR
Any	PD***	Yes or No	PD	
Any	Any	Yes	PD	

* See RECIST 1.1 manuscript for further details on what is evidence of a new lesion.  ** Only for non-randomized trials with response as primary endpoint.  *** In exceptional circumstances, unequivocal progression in non-target lesions may be accepted as disease progression.
 
Note: Patients with a global deterioration of health status requiring discontinuation of treatment without objective evidence of disease progression at that time should be reported as “symptomatic deterioration.” Every effort should be made to document the objective progression even after discontinuation of treatment.
				

**For Patients with Non-Measurable Disease (*i.e.*, Non-Target Disease)**

Non-Target Lesions	New Lesions	Overall Response
CR	No	CR
Non-CR/non-PD	No	Non-CR/non-PD*
Not all evaluated	No	not evaluated
Unequivocal PD	Yes or No	PD
Any	Yes	PD

* ‘Non-CR/non-PD’ is preferred over ‘stable disease’ for non-target disease since SD is increasingly used as an endpoint for assessment of efficacy in some trials so to assign this category when no lesions can be measured is not advised
		

11.1.5 Duration of Response

Duration of overall response: The duration of overall response is measured from the time measurement criteria are met for CR or PR (whichever is first recorded) until the first date that recurrent or progressive disease is objectively documented (taking as reference for progressive disease the smallest measurements recorded since the treatment started).

The duration of overall CR is measured from the time measurement criteria are first met for CR until the first date that progressive disease is objectively documented.

Duration of stable disease: Stable disease is measured from the start of the treatment until the criteria for progression are met, taking as reference the smallest measurements recorded since the treatment started, including the baseline measurements.

### 11.1.6 Progression-Free Survival

PFS is defined as the duration of time from start of treatment to time of progression or death, whichever occurs first.

## 12. DATA REPORTING / REGULATORY REQUIREMENTS

Adverse event lists, guidelines, and instructions for AE reporting can be found in Section 7.0 (Adverse Events: List and Reporting Requirements).

### 12.1 Data Reporting

#### 12.1.1 Method

This study will be monitored by the Clinical Data Update System (CDUS) Version 3.0. Cumulative protocol- and patient-specific CDUS data will be submitted electronically to CTEP on a quarterly basis, either by FTP burst of data or via the CDS web application. Reports are due January 31, April 30, July 31, and October 31. Instructions for submitting data using the CDUS can be found on the CTEP Web site (<http://ctep.cancer.gov/reporting/cdus.html>).

**Note:** If your study has been assigned to CDUS-Complete reporting, **all** adverse events (both routine and expedited) that have occurred on the study and meet the mandatory CDUS reporting guidelines must be reported via the monitoring method identified above. If your study has been assigned to CDUS-Abbreviated reporting, no adverse event reporting (routine or expedited) is required to be reported via CDUS.

#### 12.1.2 Responsibility for Data Submission

N/A

### 12.2 CTEP Multicenter Guidelines

N/A

### 12.3 Collaborative Agreements Language

The agent(s) supplied by CTEP, DCTD, NCI used in this protocol is/are provided to the NCI under a Collaborative Agreement (CRADA, CTA, CSA) between the Pharmaceutical Company(ies) (hereinafter referred to as “Collaborator(s)”) and the NCI Division of Cancer Treatment and Diagnosis. Therefore, the following obligations/guidelines, in addition to the provisions in the “Intellectual Property Option to Collaborator” ([http://ctep.cancer.gov/industryCollaborations2/intellectual\\_property.htm](http://ctep.cancer.gov/industryCollaborations2/intellectual_property.htm)) contained within the terms of award, apply to the use of the Agent(s) in this study:

1. Agent(s) may not be used for any purpose outside the scope of this protocol, nor can

Agent(s) be transferred or licensed to any party not participating in the clinical study. Collaborator(s) data for Agent(s) are confidential and proprietary to Collaborator(s) and shall be maintained as such by the investigators. The protocol documents for studies utilizing Agents contain confidential information and should not be shared or distributed without the permission of the NCI. If a copy of this protocol is requested by a patient or patient's family member participating on the study, the individual should sign a confidentiality agreement. A suitable model agreement can be downloaded from: <http://ctep.cancer.gov>.

2. For a clinical protocol where there is an investigational Agent used in combination with (an)other Agent(s), each the subject of different Collaborative Agreements, the access to and use of data by each Collaborator shall be as follows (data pertaining to such combination use shall hereinafter be referred to as "Multi-Party Data"):
  - a. NCI will provide all Collaborators with prior written notice regarding the existence and nature of any agreements governing their collaboration with NCI, the design of the proposed combination protocol, and the existence of any obligations that would tend to restrict NCI's participation in the proposed combination protocol.
  - b. Each Collaborator shall agree to permit use of the Multi-Party Data from the clinical trial by any other Collaborator solely to the extent necessary to allow said other Collaborator to develop, obtain regulatory approval or commercialize its own Agent.
  - c. Any Collaborator having the right to use the Multi-Party Data from these trials must agree in writing prior to the commencement of the trials that it will use the Multi-Party Data solely for development, regulatory approval, and commercialization of its own Agent.
3. Clinical Trial Data and Results and Raw Data developed under a Collaborative Agreement will be made available to Collaborator(s), the NCI, and the FDA, as appropriate and unless additional disclosure is required by law or court order as described in the IP Option to Collaborator ([http://ctep.cancer.gov/industryCollaborations2/intellectual\\_property.htm](http://ctep.cancer.gov/industryCollaborations2/intellectual_property.htm)). Additionally, all Clinical Data and Results and Raw Data will be collected, used and disclosed consistent with all applicable federal statutes and regulations for the protection of human subjects, including, if applicable, the *Standards for Privacy of Individually Identifiable Health Information* set forth in 45 C.F.R. Part 164.
4. When a Collaborator wishes to initiate a data request, the request should first be sent to the NCI, who will then notify the appropriate investigators (Group Chair for Cooperative Group studies, or PI for other studies) of Collaborator's wish to contact them.
5. Any data provided to Collaborator(s) for Phase 3 studies must be in accordance with the guidelines and policies of the responsible Data Monitoring Committee (DMC), if there is a DMC for this clinical trial.
6. Any manuscripts reporting the results of this clinical trial must be provided to CTEP by the

Group office for Cooperative Group studies or by the principal investigator for non-Cooperative Group studies for immediate delivery to Collaborator(s) for advisory review and comment prior to submission for publication. Collaborator(s) will have 30 days from the date of receipt for review. Collaborator shall have the right to request that publication be delayed for up to an additional 30 days in order to ensure that Collaborator's confidential and proprietary data, in addition to Collaborator(s)'s intellectual property rights, are protected. Copies of abstracts must be provided to CTEP for forwarding to Collaborator(s) for courtesy review as soon as possible and preferably at least three (3) days prior to submission, but in any case, prior to presentation at the meeting or publication in the proceedings. Press releases and other media presentations must also be forwarded to CTEP prior to release. Copies of any manuscript, abstract and/or press release/ media presentation should be sent to:

Email: [[contact]](mailto:[contact])

The Regulatory Affairs Branch will then distribute them to Collaborator(s). No publication, manuscript or other form of public disclosure shall contain any of Collaborator's confidential/proprietary information.

## 13. STATISTICAL CONSIDERATIONS

### 13.1 Study Design/Endpoints

Patient accrual is nearly complete for the three study cohorts: 1) squamous cell lung cancer with *NFE2L2* mutations; 2) squamous cell lung cancer with *KEAP1* mutations; 3) *KRAS* mutant lung cancer with concomitant *NFE2L2* or *KEAP1* aberration. The primary endpoint is objective response and the observed response rates in the three cohorts are: (1) 2/9, (2) 0/5, and (3) 0/5. We propose to amend the protocol to accrue an additional 10 patients for cohorts 1 and 2 to obtain preliminary information on progression free survival and greater precision for the observed response rate. Although no responses were observed in the first 5 patients in cohort 2, the genomic heterogeneity of *KEAP1* mutations in squamous cell lung cancer would indicate that further exploration is needed. Cohort 3 will be closed to accrual. The original study design is provided below.

This study utilizes a Simon two-stage design applied to each of the mutation cohorts. The primary endpoint of the study is objective response rate. The null and desired response rates are 5% and 40%. A desired response rate of 40% was selected based on past successful targeted therapy trials in lung cancer. Response rates in these biomarker-led studies are universally equal to or greater than first-line chemotherapy response rates of between 30-40%. In stage 1 of each mutation cohort, 5 patients will enter the study; if there are no responses, the study will be terminated early. If 1 or more patients respond, enrollment will be extended to 10 patients in total. At the end of stage 2, if 2 or more patients responded in either cohort, the trial will be declared effective and worthy of further testing for the respective cohort. This two-stage design yields 90% power to detect the difference at a 10% type I error rate.

Overall response rate (CR+PR) will be calculated separately for each cohort, including exact

95% confidence intervals. Duration of overall response and duration of stable disease as described in Section 11.1.5 will be calculated and summarized.

Secondary endpoints include PFS and the RPPA correlative biomarker analysis. PFS is defined from the start of treatment until progression or death, whichever occurs first. Patients will be censored at the time of the last on-study evaluation if they do not experience the event of interest. Median progression-free survival will be estimated in each cohort from start of treatment using the Kaplan-Meier method with a two-sided 95% confidence interval. The endpoint of the RPPA analysis is feasibility, defined as the ability to procure sufficient quantity and quality of tumor protein for testing. The proportion of patients with sufficient quantity and quality will be calculated, including an exact 95% confidence interval. Single target signaling changes (decrease in pS6K, p4EBP-1 as examples) will be reported as percentages relative to the baseline pre-treatment tumor sample. Larger scale pathway changes will qualitatively represented through heatmaps.

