### 13.2 Sample Size/Accrual Rate

Between 5-10 patients were initially accrued in each mutation cohort arm for a total of 20 patients. An additional 10 patients in cohorts 1 and 2 will be added for the extension phase of this study. Accrual rate is estimated at 1 patient in each arm every 2 months.

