#### **13.3.2 Evaluation of Response**

All patients included in the study must be assessed for response to treatment, even if there are major protocol treatment deviations or if they are ineligible. Each patient will be assigned one of the following categories: 1) complete response, 2) partial response, 3) stable disease, 4) progressive disease, 5) early death from malignant disease, 6) early death from toxicity, 7) early death because of other cause, or 9) unknown (not assessable, insufficient data). [Note: By arbitrary convention, category 9 usually designates the “unknown” status of any type of data in a clinical database.]

All of the patients who met the eligibility criteria (with the possible exception of those who received no study medication) should be included in the main analysis of the response rate. Patients in response categories 4-9 should be considered to have a treatment failure (disease progression). Thus, an incorrect treatment schedule or drug administration does not result in exclusion from the analysis of the response rate. Precise definitions for categories 4-9 will be protocol specific.

All conclusions should be based on all eligible patients. Subanalyses may then be performed on the basis of a subset of patients, excluding those for whom major protocol deviations have been identified (*e.g.*, early death due to other reasons, early discontinuation of treatment, major protocol violations, etc.). However, these subanalyses may not serve as the basis for drawing conclusions concerning treatment efficacy, and the reasons for excluding patients from the analysis should be clearly reported. The 95% confidence intervals should also be provided.

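### Should cohorts 1 and 2 report response separately for patients assessed after the extension was decided?

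*Combined protocol and SAP*

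**What the plan says.** Section 13.1 opens with the responses in hand: 2/9, 0/5 and 0/5. It proposes 10 more patients for cohorts 1 and 2 and closes cohort 3. The aims are preliminary information on PFS and "greater precision for the observed response rate". Cohort 2 continues, despite no responses, because *KEAP1* mutations are heterogeneous. Section 13.2 repeats the size: "An additional 10 patients in cohorts 1 and 2 will be added for the extension phase of this study".

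Section 13.1 then announces that the design the study started with follows, and sets out the Simon rule for each cohort: "5 patients will enter the study; if there are no responses, the study will be terminated early". With at least one response the cohort goes to 10, and two or more responders count as success. The paragraph ends: "This two-stage design yields 90% power to detect the difference at a 10% type I error rate".

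The analysis sentence in Section 13.1 is "Overall response rate (CR+PR) will be calculated separately for each cohort, including exact" 95% intervals. Section 13.3.2 adds: "All conclusions should be based on all eligible patients". Neither section uses the word pool, but together they give one rate over initial and extension patients. Nothing asks for the extension patients on their own.

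**The concern.** Whether a cohort grew was decided with its responses in view. Cohort 1 continued after 2/9. Cohort 2 continued after 0/5, where the rule was "if there are no responses, the study will be terminated early". Cohort 3, also 0/5, closed. A reader of the final report sees only the cohorts that grew.

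Three things could then go wrong:

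- The cohort 1 rate could be flattered by early responses that helped keep it open.
- The cohort 2 rate could be dragged down by five patients already known not to have responded.
- The 10% and 90% in the same section could be taken to describe totals of 20 and 15, for which they were not calculated.

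Response is the primary endpoint, so a misleading headline rate would matter. An extra table row looks cheap.

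**Working it through.** **Inputs.** Section 13.1: rates 5% and 40%, stages 5 then 10, success at two or more, known results 2/9 and 0/5. Section 13.2: 20 initial patients, read as 10 + 5 + 5. Schema and planned enrollment table: 40 in all. Since 20 + 10 + 10 = 40, the extension is taken as 10 in each cohort. Final sizes are then 20 in cohort 1 (9 known, 11 not) and 15 in cohort 2 (5 known, 10 not).

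**1. The plan's own figures.** P(success) = P(X1≥2) + P(X1=1)·P(X2≥1), with X1 and X2 binomial on 5 patients.

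- At 5%: 0.0226 + 0.2036 × 0.2262 = 0.0687, inside the 10% limit.
- At 40%: 0.6630 + 0.2592 × 0.9222 = 0.902, the stated 90%.

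**2. Cohort 1.** Given the recorded 2/9, the expected pooled rate is (2 + 11p)/20. Given only that both Simon gates were passed (≥1/5 and ≥2/10), it comes from exact enumeration over 10 + 10 patients. The last two columns follow the whole design: stop at 5 with no response, stop at 10 with fewer than two, otherwise go to 20.

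| True rate | Given 2/9 | Given both gates | Whole design: bias, points | Whole design: CI coverage |
|---|---|---|---|---|
| 5% | 12.8% | 13.4% | −2.5 | 99.0% |
| 10% | 15.5% | 16.8% | −4.4 | 99.0% |
| 20% | 21.0% | 24.3% | −5.6 | 99.0% |
| 30% | 26.5% | 32.4% | −4.4 | 98.3% |
| 40% | 32.0% | 41.2% | −2.6 | 97.3% |

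Given 2/9, the lean is upward below 2/9 = 22.2% and downward above it. So there is no consistent flattery; the total is simply pulled toward what was seen. Over the whole design the plain proportion errs low.

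Conditional coverage in cohort 1 is short near 5%. There, 4/20 (5.7% to 43.7%) misses and 3/20 (lower limit 3.2%) does not. Coverage given 2/9 is therefore P(at most 1 response in 11) = 0.95^11 + 11 × 0.05 × 0.95^10 = 0.569 + 0.329 = 89.8%. Given both gates it is 85.6%.

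**3. Cohort 2.** Given 0/5, the expected pooled rate is 10p/15: 3.3%, 6.7%, 13.3% and 26.7% at true 5%, 10%, 20% and 40%. Conditional coverage is 95.4% to 99.9% at 5%, 10%, 20%, 30% and 40%, but it dips between those points. At 32%, for instance, 0/15 and 1/15 (upper limit 31.9%) both miss, so coverage is 1 − 0.68^10 − 10 × 0.32 × 0.68^9 = 1 − 0.021 − 0.099 = 87.9%. This is what fixing five zeros does. If the cohort would have been extended whatever its result, as the heterogeneity argument suggests, the rate over all 15 is unbiased.

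**4. Error rates.** Suppose the two-responder rule were carried onto the totals. At a true 5% the chance of meeting it would be:

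- Cohort 1, first gate kept: 0.0226 + 0.2036 × (1 − 0.95^15) = 0.0226 + 0.2036 × 0.5367 = 13.2%.
- Cohort 2, stop set aside: 1 − 0.95^15 − 15 × 0.05 × 0.95^14 = 1 − 0.463 − 0.366 = 17.1%.

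Both need a misreading. Section 13.1 places the rule at the end of stage 2, with 10 patients in total, under a sentence marking it as the design the study began with.

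**5. What a separate row would show.** For 2/10 the exact interval is 2.5% to 55.6%; for 4/20 it is 5.7% to 43.7%. The extension-only interval is 53.1 points wide against 38.0, so it works against the stated aim of precision. Nor would a row of 10 extension patients in cohort 1 separate known from unknown, because the split there is 9 and 11.

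**The case for a change.** The best case for a change is that readers meet the result only because the cohort was extended, so conditional behaviour is what concerns them, and design-wide averages do not describe cohort 2, where the stopping rule was set aside. Patients assessed after the decision are the only ones whose rate has expectation p whatever came before. Subtracting 2/9 and 0/5 from the totals needs the protocol in hand, and replacement under Section 5.5 may shift the denominators. The row costs a line, and the pooled rate would stay.

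Much of this is true. The conditional means are right, and the conditional intervals do fall short at some true rates. The whole-design figures also assume an extension after every pass, which was not planned from the start. But the remedy sits beside the pooled rate and leaves it alone, so no planned estimate or conclusion would differ. The known counts are on record in Section 13.1, and an analyst with assessment dates can produce the split whenever it is wanted.

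**Conclusion.** No change is needed. Following Sections 13.1 and 13.3.2 as written gives an all-eligible rate with an exact interval, which suits a small descriptive extension meant to add precision and early PFS information. Given 2/9, the cohort 1 rate is expected to be about 8 points high at a true 5% and 8 points low at a true 40%. Cohort 2 is one third low given its five zeros, which are legitimate data and do not reflect selection on good results. Over the whole design, coverage at the five rates tabulated is 97.3% to 99.0%.

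This rests on 10 extension patients per cohort, cohort 1 filled to 10 first, and the Simon decision confined to its 5 + 5 patients. Showing patients known at the amendment (9 and 5) beside those assessed later (11 and 10) would be a reasonable courtesy in the report, but it is a presentation choice and corrects nothing.
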